### 9.2. Adverse Events

#### 9.2.1. Adverse Event Definitions

A TEAE is any AE either reported for the first time or worsening of a pre-existing event after the first dose of study drug and up to 30 days after the last dose of study drug. Analysis of AEs will be limited to TEAEs, but data listings will include all AEs regardless of their timing in relation to study drug administration. For purposes of analysis, all AEs will be considered TEAEs unless the AE can unequivocally be defined as not treatment emergent.

A TEAE during the PC period is any AE with a start time after the first dose of study drug during the PC period and until the end of the safety follow-up or prior to the first dose during the EXT period for participants who entered the EXT period.

A TEAE during the EXT period is any AE with a start time after the first dose of study drug during the EXT period and until the end of the EOT2.

For participants who received only povorcitinib 15, 45, or 75 mg during the overall period, a TEAE is any AE with a start time after the first dose of study drug during the PC period and until the EOS.

Adverse events will be tabulated by MedDRA PT and SOC. Severity of AEs will be graded using the National Cancer Institute CTCAE v5.0. The CTCAE reporting guidelines and grading details are available on the Cancer Therapy Evaluation Program website.

The subset of AEs considered by the investigator to be related to study drug will be considered to be treatment-related AEs. If the investigator does not specify the relationship of the AE to study drug, the AE will be considered to be treatment related. The incidence of AEs and treatment-related AEs will be tabulated. Serious treatment-related TEAEs will also be tabulated.

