 - There may be situations in which an SAE has occurred and the investigator has minimal information to include in the initial report. However, the causality assessment is one of the criteria used when determining regulatory reporting requirements. **Therefore, it is very important that the investigator always make an assessment of causality based on the available information for every event before the initial transmission of the SAE.**
 - The investigator may change their opinion of causality in light of follow-up information and submit the updated causality assessment.

Follow-Up of Adverse Events and Serious Adverse Events

- The investigator is obligated to perform or arrange for the conduct of supplemental measurements and/or evaluations as medically indicated or as requested by the sponsor to elucidate the nature and/or causality of the AE or SAE as fully as possible. This may include additional laboratory tests or investigations, histopathological examinations, or consultation with other health care professionals.
- Once an AE is detected, it should be followed in the Adverse Events Form in the eCRF until it has resolved or until it is judged to be permanent; assessment should be made at each visit (or more frequently if necessary) of any changes in severity, the suspected relationship to the study drug, the interventions required to treat the event, and the outcome.
- When the severity of an AE changes over time for a reporting period (eg, between visits), each change in severity will be reported as a separate AE.
- If a participant dies during participation in the study or during a recognized follow-up period, the investigator will provide the sponsor with a copy of any postmortem findings, including histopathology.
- Updated SAE information will be recorded in the originally completed eCRF and reported to Incyte Pharmacovigilance (in the SAE EDC CRF) until resolution, stabilization, the event is otherwise explained, or the participant is lost to follow-up.
- Any updated SAE data (including SAEs being downgraded to nonserious) will be submitted to the sponsor (or designee) within 24 hours of receipt of the information.

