10.4.3. Safety Analyses

Safety analyses will be conducted for the safety population. Adverse events will be coded by the MedDRA dictionary, and TEAEs (ie, AEs reported for the first time or worsening of a pre-existing event after first dose of study drug and until 60 days after the last dose of study drug) will be tabulated by preferred term and system organ class for all events, related events, and events of Grade 3 or higher. The Protocol-defined ECIs and AESIs will be tabulated by preferred term and Protocol-defined categories for all events. Quantitative safety variables (eg, laboratory values, vital signs) and their changes from baseline will be summarized with descriptive statistics. Clinically notable abnormal values will be flagged and tabulated based on predefined criteria.

The subset of AEs considered by the investigator to have a relationship to study drug will be considered to be treatment-related AEs. If the investigator does not specify the relationship of the AE to study drug, then the AE will be considered treatment-related. The incidence of AEs and treatment-related AEs will be tabulated.

The clinical laboratory data will be analyzed using summary statistics; no formal treatment group comparisons are planned. In addition, distributions of key laboratory parameters may be plotted over time; these values will also be classified into CTCAE v5.0 toxicity grades and tabulated. Descriptive statistics and mean change from baseline will be determined for vital signs at each assessment time. Vital sign results will be reviewed for clinically notable abnormalities. Descriptive statistics and mean change from baseline will be determined for each ECG parameter at each assessment time.

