### **5.2. Treatment Groups**

Table summaries, unless otherwise indicated, will present data by treatment group. The results will be summarized and presented separately for the PC period, EXT period, post-treatment period, and overall period (for safety only) unless otherwise specified.

For the PC period, the treatment groups will be placebo and povorcitinib 15, 45, and 75 mg.

For the EXT period and the post-treatment follow-up period, the treatment groups will be as follows:

- Placebo to povorcitinib 15 mg
- Placebo to povorcitinib 45 mg
- Placebo to povorcitinib 75 mg
- Povorcitinib 15 mg
- Povorcitinib 45 mg
- Povorcitinib 75 mg

For the overall period, the treatment groups will be povorcitinib 15, 45, and 75 mg.

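### Extension-period TEAEs are defined by start time alone, so an event from the placebo-controlled period that only drops in grade after the first extension dose counts as a new TEAE

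*SAP*

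**What the plan says.** SAP section 9.2.1 opens with a general definition: "A TEAE is any AE either reported for the first time or worsening of a pre-existing event after the first dose of study drug". Protocol section 10.4.3 has the same test: "AEs reported for the first time or worsening of a pre-existing event after first dose of study drug". Both contain a new-or-worse condition, and both measure it from the first dose of study drug.

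The SAP then gives a rule for each period. For the PC period: "A TEAE during the PC period is any AE with a start time after the first dose of study drug during the PC period". For the extension: "A TEAE during the EXT period is any AE with a start time after the first dose of study drug during the EXT period". Neither sentence repeats the new-or-worse condition. The section also sets a default: "all AEs will be considered TEAEs unless the AE can unequivocally be defined as not treatment emergent".

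Protocol section 9.3 governs how records are created. When severity changes over a reporting period, for example between visits, "each change in severity will be reported as a separate AE".

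SAP section 5.2 displays the EXT period in six groups. Three of them are placebo switchers, such as "Placebo to povorcitinib 15 mg". SAP section 9.2.2 counts participants, not events. For laboratory and other measured safety data, SAP section 4.1.3 resets the EXT baseline of participants who cross over to the last value before their first EXT dose.

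**The concern.** The recording rule and the period rule were written separately and do not fit together. The first can turn one clinical event into several records, each with its own start. The second admits a record because of its start. An event that began on placebo and is resolving can therefore be shown as something that emerged on povorcitinib.

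Placebo switchers are the only participants newly exposed to povorcitinib in the EXT period, so their columns are where a reader looks for early effects of starting the drug. These groups are small, and a single misattributed case is visible in the percentages. For participants who stay on povorcitinib, the same event can be reported in both the PC and the EXT tables as if it had occurred twice.

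**Working it through.** The plan states no figure to reproduce. The check is of the rules, followed by a small calculation of scale.

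**Step 1: the rules side by side.**

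- First EXT dose: the day after the Week 12 visit (Protocol section 6.5.1). With Week 12 on Day 85, this is Day 86.
- Literal EXT rule: count a record if it starts after the first EXT dose.
- Reference rule: count a record only if the event first began after that dose, or if the grade is above the grade held before it.

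Four illustrative participants:

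| Participant | Records (grade, days) | Literal rule | Reference rule |
|---|---|---|---|
| A | Grade 2, Days 20–80 | no | no |
| B | Grade 3, Days 70–90; Grade 2, Days 90–110 | **yes** | no |
| C | Grade 1, Days 80–95; Grade 2, Days 95–120 | yes | yes |
| D | Grade 2, Days 100–110 | yes | yes |

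The rules differ only for B, whose event began before the switch and then improved.

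**Step 2: does the general definition remove B?** It asks whether the event was first reported, or worsened, after the first study dose. If B is a placebo switcher, that dose was placebo on Day 1. B's event began on Day 70, so it already qualifies. Applying the general sentence as an extra filter leaves B in. The missing element is a grade reference at the first EXT dose. Neither document supplies one, and neither links records that belong to one event. The default towards counting does not help either.

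**Step 3: scale.**

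- Placebo group: 136 / 4 = 34 (Protocol section 10.1).
- Switch groups at 1:1:1 (Protocol section 2.2.1): 34 / 3 = 11.3, so 11 or 12 each if everyone continues.
- One false case: 1/11 = 9.1 points; 1/12 = 8.3 points; 1/34 = 2.9 points if the switchers are pooled.

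**Step 4: chance of at least one case (assumed inputs).** Let q be the share of switchers with an event ongoing at the switch that later drops a grade and is recorded anew. The documents give no value for q. The chance of at least one such participant in a group of 11 is 1 − (1 − q)^11:

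| Assumed q | Expected among 34 | Chance of at least one in 11 |
|---|---|---|
| 2% | 0.7 | 20% |
| 5% | 1.7 | 43% |
| 10% | 3.4 | 69% |

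These figures show only that small shares matter in small groups. They do not estimate the inflation of any table row, because some of these participants will also have a genuine EXT TEAE.

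**The case against.** **Improvement is not named.** Protocol section 9.3 speaks of changes in severity without saying that a fall in grade opens a record. Other text leans the other way. Protocol section 8.3.1 and the start of section 9.3 tell sites to record events that begin or worsen. Section 9.3 also has an event followed on its form until it resolves, and offers an outcome category for events that are resolving. Detail is left to eCRF guidelines that are not part of these documents. This stands as a limit on frequency: if sites do not open a record on improvement, the problem does not arise. It does not cancel the rule, which covers every change.

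**The period sentences may only allocate events.** They can be read as assigning already qualified TEAEs to periods, leaving the general test in force. This stands for events that predate all study drug. A reader might infer that a screening event which improves after Day 1 becomes a PC TEAE. The documents do not clearly support that, because such an event is neither new nor worse after the first dose and can be excluded under the general sentence. The argument does not help at the switch, for the reason in Step 2 of the working.

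**The reach is limited.** This is largely right:

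- Participants are counted, so someone with another EXT TEAE adds nothing to the any-TEAE row. The preferred-term row can still be wrong.
- A fall from Grade 3 to 2, or from 2 to 1, cannot enter the Grade 3 or higher tables. A fall from Grade 4 to 3 could.
- The overall-period tables cover only participants who received povorcitinib alone, so placebo-onset events cannot enter them. Splitting an event that began on treatment does not change a participant count there.
- For serious events, Protocol section 9.4 sends recurrence, complication or progression back to the original event, so the effect on SAE counts is unclear.
- The columns show the prior placebo exposure, the listings contain all AEs, and the final analysis makes no statistical comparison with placebo.

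**Conclusion.** The point holds on the literal text, within limits. A PC-period event that only drops in grade after the first EXT dose meets the EXT TEAE rule. It is then tabulated under a placebo-to-povorcitinib group, or appears in both period tables for a participant continuing povorcitinib. The mechanism can add cases but cannot remove them. It affects the descriptive EXT tables, mainly the preferred-term rows, and the any-TEAE row only for participants with no other EXT TEAE. The efficacy analyses are untouched.

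One false case is 8.3 to 9.1 percentage points in a group of 12 or 11, assuming all 34 placebo participants enter the EXT period. A reader might go on to infer that EXT TEAE rates on povorcitinib are overstated by some stated percentage. The documents do not support that: they contain no AE rates, no information on how often sites record improvement separately, and no way to allow for overlap with genuine EXT TEAEs.

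Correction is still worthwhile. The rule as written can attribute resolving placebo-period events to povorcitinib. The SAP already resets the safety baseline at the switch for measured data, and the AE rule has no equivalent.

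**What to change.** In SAP section 9.2.1:

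1. State that the period rules apply in addition to the first-report-or-worsening test.
2. Link records created by a severity change into one event, using the same preferred term and contiguous dates. Add a rule for partial AE dates, since SAP section 4.1.4 gives none for AE start dates.
3. Count a linked event as an EXT TEAE only if its first onset is after the first EXT dose, or if its grade in the EXT period exceeds the grade immediately before that dose. An event that falls and then returns to its pre-switch grade is not counted.

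The third item is essential, because the first does not exclude events that began on placebo.

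The cost is SAP wording, a prespecified matching rule and a linking step in the AE program. Matching on term and dates may occasionally join two separate events or split one, so the rule should be fixed before the EXT data are tabulated. No new data are needed and site conduct does not change.

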#### 9.2.2. Adverse Event Summaries

Adverse events will be summarized by treatment group for the Safety Population during the PC period, for the EXT-Evaluable population during the EXT period, and overall for participants who received only povorcitinib 15, 45, or 75 mg during the study.

An overall summary of AEs will include the following:

- Number (%) of participants reporting any TEAEs
- Number (%) of participants reporting any serious TEAEs
- Number (%) of participants reporting any Grade 3 or higher TEAEs
- Number (%) of participants reporting any treatment-related TEAEs
- Number (%) of participants who temporarily interrupted study treatment because of TEAEs
- Number (%) of participants who permanently discontinued study treatment because of TEAEs
- Number (%) of participants who had a fatal TEAE
- Number (%) of participants who had a TEAE requiring concomitant medication

The following summaries will be produced by MedDRA term (if 10 or fewer participants appear in a table, a listing may be appropriate):

- Summary of TEAEs by MedDRA SOC and PT
- Summary of TEAEs by MedDRA PT in decreasing order of frequency
- Summary of TEAEs by MedDRA SOC, PT, and maximum severity
- Summary of TEAEs by MedDRA SOC, PT, and CTCAE grade category
- Summary of Grade 3 or higher TEAEs by MedDRA SOC and PT
- Summary of Grade 3 or higher TEAEs by MedDRA PT in decreasing order of frequency
- Summary of serious TEAEs by MedDRA SOC and PT
- Summary of serious TEAEs by MedDRA PT in decreasing order of frequency
- Summary of treatment-related TEAEs by MedDRA SOC and PT
- Summary of treatment-related TEAEs by MedDRA PT in decreasing order of frequency
- Summary of Grade 3 or higher treatment-related TEAEs by MedDRA SOC and PT
- Summary of treatment-related serious TEAEs by MedDRA SOC and PT
- Summary of TEAEs with a fatal outcome by MedDRA SOC and PT
- Summary of TEAEs leading to dose interruption by MedDRA SOC and PT
- Summary of TEAEs leading to discontinuation of study drug by MedDRA SOC and PT

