1. PROTOCOL SUMMARY

Protocol Title: A Phase 2, Double-Blind, Randomized, Placebo-Controlled, Dose-Ranging, Efficacy, and Safety Study of Povorcitinib in Participants With Chronic Spontaneous Urticaria

Brief Title: A Study Evaluating the Efficacy and Safety of Povorcitinib in Adults With Chronic Spontaneous Urticaria

Protocol Number: INCB 54707-207

Objectives and Endpoints:

Table 1 presents the primary and secondary objectives and endpoints.

Table 1: Primary and Secondary Objectives and Endpoints

Objectives	Endpoints
Primary	
To evaluate the efficacy of povorcitinib in participants with CSU.	Change from baseline in the UAS7, defined as the 7-day sum of the individual, daily recorded scores for HSS and ISS, at Week 12.
Secondary	
To further evaluate the efficacy of povorcitinib in participants with CSU.	
• Proportion of participants who achieve $UAS7 \leq 6$ (controlled disease) at Week 12.• Time to first achievement of $UAS7 \leq 6$ (controlled disease) during the PC period.• Proportion of participants with $UAS7 = 0$ at Week 12.

Overall Design:

Table 2 presents the key study design elements. Further study details are presented after the table.

Table 2: Key Study Design Elements

Study Phase	Phase 2
Clinical Indication	Treatment of patients with CSU that is inadequately controlled by second-generation H1 antihistamines.
Population	Participants aged 18 to 65 years who have had a diagnosis of CSU for ≥ 3 months that is inadequately controlled by second-generation H1 antihistamines. Inadequately controlled CSU is defined as UAS7 ≥ 16 during the 7 days prior to randomization.
Number of Participants	Approximately 136 participants will be randomized 1:1:1:1 to 1 of 4 treatment groups (≈ 34 participants per group). Participants will be stratified by previous treatment of CSU with an anti-IgE biologic agent (yes or no).
Study Design	Multicenter, parallel-group, double-blind, randomized, placebo-controlled, dose-ranging study.
Estimated Duration of Study Participation	It is estimated that an individual will participate for approximately 48 weeks (11 months) as follows: 
 • Screening: up to 28 days • PC period (double-blinded): 12 weeks • EXT period (double-blinded): 24 weeks • Post-treatment follow-up: 60 days (± 7 days) after last dose of study drug
DSMB	Yes (internal)
CAC	Yes
Coordinating Principal Investigator	[name]. [name]

Treatment Groups and Duration:

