### 9.2.3. Adverse Events of Special Interest

Incyte defines AESIs and ECIs as a subset of TEAEs that investigators must rapidly communicate to Incyte for further evaluation. The AESI categories and the search strategy of each AESI are provided in Table 6. A separate SMQ file that includes all search strategies will be provided separately. The number and percentage of participants who have any AESI will be summarized.

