#### **9.3.2. Laboratory Value Summaries**

All test results and associated normal ranges from central laboratories will be reported in SI units. All tests with numeric values will have a unique unit per test. Any laboratory test results and associated normal ranges from local laboratories will be converted to SI units.

When there are multiple nonmissing laboratory values for a participant's particular test at a scheduled visit, central laboratory values have higher priority over local laboratory values. If a tie still exists, the laboratory value with the smallest laboratory sequence number will be used in by-visit summaries. In addition, box plots will be provided for creatine kinase, hemoglobin, hematocrit, platelet count, high-sensitivity C-reactive protein, IgE, lymphocyte absolute count, neutrophil absolute count, white blood cell count, basophil cell count, eosinophil cell count, total cholesterol, HDL, LDL, HDL/LDL ratio, ALT, and AST.

For test results that will be summarized with available normal ranges, the number and percentage of participants with laboratory values that are low (but never high), normal, high (but never low), and both low and high will be calculated for each test. This shift summary will be produced for each test. The denominator for the percentage calculation will use the number of participants in the baseline category (ie, low, high, normal, missing) as the denominator for the percentage in each of the categories during the study.

Severity grades will be assigned to laboratory test values based on the numerical component of CTCAE v5. Shift tables will also be presented showing change in CTCAE grade from baseline to the worst grade postbaseline. Separate summaries for abnormally high and abnormally low laboratory values will be provided when the laboratory parameter has both high and low grading criteria. The denominator for the percentage calculation will be the number of participants in the baseline category. The number of participants who experienced worsening of laboratory abnormalities will be summarized by maximum severity.

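### Adverse events are planned only as crude percentages over windows of about 12, 24 and up to 45 weeks, so they are not comparable across periods; exposure-adjusted rates should be added

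*SAP*

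**What the plan says.** **Measure.** The overall AE summary in SAP 9.2.2 starts with "Number (%) of participants reporting any TEAEs", and its other lines take the same form. The remaining AE displays are tabulations by system organ class, preferred term, grade, relatedness and action taken. For events of special interest (AESIs), SAP 9.2.3 states: "The number and percentage of participants who have any AESI will be summarized". SAP 9.2.4 treats events of clinical interest (ECIs) in the same way, or lists them. Protocol 10.4.3 also plans tabulations only.

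**Windows.** The Protocol summary gives "PC period (double-blinded): 12 weeks" and "EXT period (double-blinded): 24 weeks", followed by about 60 days of follow-up. SAP 9.2.1 then defines:
- PC: from first dose "until the end of the safety follow-up or prior to the first dose during the EXT period", the second limit applying to those who continue into EXT.
- EXT: from first EXT dose to the Week 36 end-of-treatment visit.
- Overall, for participants who only ever received povorcitinib: "a TEAE is any AE with a start time after the first dose of study drug during the PC period and until the EOS".

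The general TEAE definition in SAP 9.2.1 stops 30 days after the last dose. Protocol 10.4.3 uses 60 days.

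**Columns.** SAP 5.2 tabulates the periods separately. Placebo appears only in PC; the overall groups are the three povorcitinib doses.

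**Exposure.** SAP 6.4 derives and summarizes treatment duration, but nothing in the SAP uses it as an adverse-event denominator.

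**Laboratory.** SAP 9.3.2 adds worst-grade tables: "Shift tables will also be presented showing change in CTCAE grade from baseline to the worst grade postbaseline".

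**The concern.** A percentage of participants with at least one event grows with the time over which events are counted. Here that time differs two- to almost fourfold between tables, and the plan offers no measure on a common scale.

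This matters because most of the drug experience lies outside the PC period. At the planned 34 per arm with full retention, povorcitinib time is 102 × 12 = 1,224 weeks in PC and 136 × 24 = 3,264 weeks in EXT. EXT therefore holds 3,264/4,488 = 73% of about 86 person-years. Placebo supplies 34 × 12 = 408 weeks, about 8 person-years.

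Protocol Table 4 describes thromboembolic events, serious infection and malignancy as risks seen with other JAK inhibitors whose link to povorcitinib is not established, and Protocol 9.6.1 makes them AESIs. Whether their incidence changes with time on drug is a basic question, and percentages over unequal windows cannot answer it. Follow-up also varies within a table. A participant who stops early has a shorter window, and a PC participant who does not enter EXT is counted through safety follow-up, beyond the last dose.

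**Working it through.** **1. Window lengths.** The Protocol summary states about 48 weeks of participation. Screening 4 + PC 12 + EXT 24 + follow-up 60/7 = 48.6 weeks, which agrees. It follows that:
- first dose to end of study: 36 + 60/7 = 44.6 weeks;
- with a 30-day cut-off instead: 36 + 30/7 = 40.3 weeks;
- PC window for a participant who takes 12 weeks of drug and does not enter EXT: up to 12 + 60/7 = 20.6 weeks.

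**2. No drug effect, constant hazard.** The documents give no 12-week placebo risk p, so p is an assumption and a range is shown. With h = −ln(1 − p)/12 per week, the risk over w weeks is 1 − exp(−h·w).

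| 12 weeks (assumed) | EXT, 24 weeks | Overall, 40.3 weeks | Overall, 44.6 weeks |
|---|---|---|---|
| 2% | 4.0% | 6.6% | 7.2% |
| 5% | 9.8% | 15.8% | 17.3% |
| 10% | 19.0% | 29.8% | 32.4% |
| 20% | 36.0% | 52.7% | 56.3% |
| 40% | 64.0% | 82.0% | 85.0% |
| 60% | 84.0% | 95.4% | 96.7% |

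Relative to 12 weeks, the ratio is 1.4 to 2.0 for EXT and 1.6 to 3.6 for the 44.6-week window.

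**3. Hazard allowed to fall.** Let the hazard after Week 12 be r times the PC hazard.
- EXT risk is 1 − exp(−24·r·h). It exceeds 1 − exp(−12·h) only if r > 0.5. With p = 40%, EXT gives 40.0% at r = 0.5, 33.5% at r = 0.4 and 22.5% at r = 0.25.
- Overall risk is 1 − exp(−12·h − r·h·(24 + 60/7)). This cannot be below the 12-week risk, because the overall window contains the PC window for the same randomized participants. At r = 0.25 it is 57.6% against 40%, and 8.2% against 5%.

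**4. Sampling at 34 per arm, constant hazard.** These are statements about expectation. The chance that the observed percentage exceeds the placebo one is 70% (EXT) and 93% (overall) for a 5% event, and 53% and 77% for a 2% event.

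**5. What a rate does.** Participants with a first event per 100 person-years is 100 × 52.18 × h. For 12-week risks of 5%, 10% and 40% this is 22.3, 45.8 and 222. Under a constant hazard and no effect the value is the same in every window, so the apparent ratios return to 1.0.

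**6. Worst-grade laboratory shifts.** Protocol Table 3 schedules chemistry and hematology at Weeks 4, 8 and 12 in PC (3 draws) and at Weeks 16 to 36 in EXT (6 draws). With an assumed chance q of an abnormal grade per draw and independent draws, the risk is 1 − (1 − q)^k:
- q = 2%: 1 − 0.98³ = 5.9% and 1 − 0.98⁶ = 11.4%;
- q = 5%: 14.3% and 26.5%;
- q = 10%: 27.1% and 46.9%.

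Independence is the unfavourable case. Positive correlation within a participant narrows the gap, and perfect correlation removes it.

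**The case against.** **The plan makes no cross-period comparison.** Periods are tabulated separately, and Protocol 10.4 says the final analysis carries no statistical comparison with placebo. The controlled contrast is the PC table, with placebo and three doses under one window rule. This stands: the difficulty arises when someone reads across tables. But readers will want to know how longer exposure compares, and the SAP gives them nothing suited to it.

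**Stronger readings a reader might infer.**
- *Both the EXT and overall percentages exceed placebo by construction.* Not for EXT. It is a separate, later window in participants who stayed to be dosed there, and early-onset events could reverse the order.
- *The overall tables can be read only against 12-week placebo.* They show 15, 45 and 75 mg side by side under one window rule, which allows a dose comparison.
- *Early stopping hides events.* Only partly. Protocol 8.3.1 and 8.8.1 collect adverse events for at least 60 days after the last dose.
- *Laboratory reporting as a whole is inflated.* SAP 9.3.1, 9.3.3 and 9.3.4 summarize values by visit, which does not accumulate over draws. Only the worst-grade shifts do.

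**Rates can mislead too.** Take p = 40%, r = 0.25 and no drug effect. The PC rate is 222 per 100 person-years and the EXT rate 0.25 × 222 = 55.5. The pooled overall rate is about 116: 0.576 first events per participant over 25.9 weeks at risk, × 52.18 × 100. Set beside 12-week placebo, 116 is false reassurance. This stands and shapes the fix.

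**Little precision for rare events.** With zero events the exact 95% upper limit is 3.69 divided by person-years: about 47 per 100 person-years for placebo (7.8 person-years) and 13 per dose overall (34 × 44.6/52.18 = 29). This also stands, and SAP 9.1 and 9.2.2 allow listings for sparse events.

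**Unseen shells.** Table shells are in a separate document, so the absence of rates is established for the SAP text and its table list only.

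**Conclusion.** The point holds as a modest, inexpensive improvement. Adverse-event percentages in this SAP are not comparable across periods, and no exposure-adjusted measure is planned. Under no drug effect, the overall povorcitinib percentage exceeds the 12-week placebo percentage in expectation. The EXT percentage does so unless the hazard after Week 12 falls to half or less of its earlier value. For an assumed 12-week risk of 10% and a constant hazard the sizes are 19.0% (EXT) and 32.4% (overall), or 29.8% overall with a 30-day cut-off.

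These figures rest on assumed 12-week risks and full-length windows. The overall figure also depends on which of the 30-day, 60-day and end-of-study limits governs, which the documents leave unresolved.

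The documents do not support the inference that the controlled safety comparison is invalid. Placebo and the doses are compared concurrently in PC, with some variation in follow-up from discontinuation. The laboratory point is secondary and confined to the worst-grade shift tables.

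**What to change.** 1. Keep the crude percentages. Beside them give exposure-adjusted incidence rates: participants with a first event per 100 person-years at risk, time censored at first event or end of the TEAE window, with a 95% CI. Do this for any, serious and Grade 3 or higher TEAEs and for each AESI and ECI category. In SAP Appendix A these are Tables 3.2.1.x, 3.2.6.x, 3.2.8.x, 3.2.17.x and 3.2.20.x and their overall (.3) versions.
2. Show the rates separately for PC (all four arms) and EXT, as well as overall by dose. A falling hazard is then visible, and the pooled overall rate is less likely to be set against 12-week placebo.
3. Reconcile the 30-day (SAP 9.2.1, general), 60-day (Protocol 10.4.3) and end-of-study (SAP 9.2.1, overall) limits, so that events and person-time share one defined window per period.
4. Footnote the worst-grade shift tables with the number of postbaseline draws in each period.

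The cost is SAP wording and a rate column in a few tables, from dates already collected; no trial procedure changes. The drawbacks are imprecise rates for rare events and the assumption of a roughly constant hazard within each period.
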